Group 2 will receive bisoprolol with the dose titrated to a maximum, and then, if necessary, the patient will be shifted to the combination therapy (Step 2 – adding an ACE inhibitor).

After randomization to moxonidine and bisoprolol groups (V1), patients start treatment with 0.4 mg moxonidine QD or 5 mg bisoprolol QD. If the target BP (<140/90 mmHg) is reached in 2 weeks, the patient continues taking the medication at the same dose. If the target BP is not reached in 2 weeks, the moxonidine dose is increased to 0.6 mg QD, the dose of bisoprolol is increased to 7.5 mg QD. If the target BP is not reached in 2 weeks of treatment with the increased doses, an ACE inhibitor (perindopril) at a dose of 10 mg/day is added at the 8th week of the study. In case of intolerance to perindopril, losartan at a dose of 50 mg/day will be administered.

During the study, the patient will have parameters of efficacy, tolerability and safety of the therapy with moxonidine or bisoprolol regularly assessed.

The study design is shown in Figure 1.

Figure 1. The overall study design

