### 3.4 Schedule of the study procedures

Prior to the study enrollment, examination to assess conformity with the inclusion/exclusion criteria, to obtain baseline data and ensure washout period (if necessary) will be carried out for a patient. After enrollment and initiation of the investigated treatment, the study procedures will be conducted to assess product tolerability, safety, efficacy and patient compliance. All scheduled visits are mandatory. Washout period will be carried out only for patients with prior antihypertensive therapy. Each patient is to sign the informed consent prior to any study activities including screening / “examination to assess conformity with the in- and exclusion criteria.

Schedule of the study procedures is presented in Table 2.

	Visit 0 Screening	Visit 1	Visit 2	Visit 3	Visit 4
	Day-14...-1	Day 0	Week 8	Week 24	Week 48
Drug administration		+	+	+	+
Dose titration / treatment adjustment		+	+	+	
BP / HBR / Patients' diary analysis	+	+	+	+	+
ECG, K, Na	+			+	
Creatinine	+			+	
ALT/AST	+			+	
Parathyroid hormone	+				
X-ray densitometry, BMD	+				+
Total calcium, Phosphorus	+			+	+
PWV		+			+
IMT + evaluation of subclinical atherosclerosis		+			+
Telomerase activity		+			+
Osteocalcin		+		+	+
Collagen type 1 C-telopeptide		+		+	+
Osteoprotegerin, RANKL		+			+
Safety Information	+	+	+	+	+

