### **Treatment regimens**

- **Group 1** patients receive moxonidine with dose titration up to the maximum, then a patient may be switched to the combination therapy, if necessary (step 2 - adding an ACE inhibitor).
- **Group 2** patients receive bisoprolol with dose titration up to the maximum, then a patient may be switched to the combination therapy, if necessary (step 2 - adding an ACE inhibitor).

The investigator will provide a Group 1 patient with moxonidine 0.4 mg in the amount required for 56 days of treatment plus 7 extra days and additionally moxonidine 0.2 mg in an amount required for 42 days of treatment if the dose is titrated up to 0.6 mg/day.

The patient will take the first moxonidine tablet immediately during the visit after all the visit procedures are completed. The patient will be instructed to take 1 tablet of moxonidine 0.4 mg in the morning, daily. The next visit will be scheduled in week 8 after the enrollment visit (in 56 days  $\pm$  5 days after the enrollment visit).

The patient will be asked to bring all the blisters of investigated product (empty, started and not started blisters) to every visit after the study initiation.

The investigator will give the patient blood pressure self-monitoring diary which is to be used by the patient to daily document her BP values and to bring it to every subsequent visit.

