### **3.6.4 Visit 2 (V2)**

Visit 2 is conducted at week 8 after the enrollment visit. The investigator will document the disease history since the last visit, including all adverse events, changes in concomitant treatment, and changes in concomitant medications doses, if any.

The investigator will analyze the effectiveness of the therapy according to the patient's BP self-monitoring diary data.

The investigator measures blood pressure and heart rate in a sitting position after 5 minutes of rest. **Two** measurements are done; the average value of the measurements is documented. BP is measured on the same arm during the entire study.

The investigator analyzes the patient's compliance based on the number of returned tablets.

The investigator evaluates response to the treatment (target BP reaching), documents it in source documents and decides on further treatment of the patient. If target BP has not been reached, the patient's investigated product dose is titrated according to the study design. If the target BP has been reached, the patient continues with the current treatment until the next visit.

The investigator will invite the patient to the next visit (visit V3) scheduled for week 24 after the enrollment visit (168 days  $\pm$  5 days after the enrollment visit); the patient will be asked to return the investigated medication blisters (empty, started and not started blisters). The patient will be instructed to start taking the provided product the next day morning, 1 tablet per day. The patient will be instructed to report any adverse events (if applicable) to the investigator.

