### 3.8 Study products

Investigated products, moxonidine and bisoprolol, will be provided by the Sponsor, packaged and labeled in accordance with local regulatory requirements.

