### 3.8.3 Additional medications

**3.8.3.1 Name:** angiotensin converting enzyme inhibitor. INN: perindopril

Produced by Les Laboratoires Servier Industrie

**Pharmaceutical form:** film-coated tablets.

One tablet contains perindopril arginine 10 mg as an active substance. Other ingredients: lactose monohydrate, magnesium stearate, maltodextrin, hydrophobic colloidal silica, sodium starch glycolate (type A), glycerol, hypromellose, macrogol 6000, titanium dioxide (E171), copper chlorophyllin (E141 II).

**Posology and method of administration:** once a day, orally, before a meal, preferably in the morning.

**Duration of treatment:** perindopril 10 mg is prescribed to postmenopausal patients with hypertension and osteopenia who have not reached target BP (<140/90 Hgmm) by V2 (week 8). Patients should take the medication until study week 48 (V4).

**3.8.4 Name:** angiotensin II receptor blocker. INN: Losartan

Produced by Berlin-Chemie, Germany.

**Pharmaceutical form:** coated tablets.

Each tablet contains 50 mg of losartan.

**Posology and method of administration:** Bisoprolol is taken orally, once a day, regardless of meals. The product is prescribed to postmenopausal patients with hypertension and osteopenia non-responsive to moxonidine or bisoprolol monotherapy for 4 weeks and intolerant to perindopril. Patients should take the medication until study week 48 (V4).

**3.8.5. Name:** calcium and vitamin D. INN: Calcium carbonate + cholecalciferol

Produced by Nycomed Pharma, Norway.

**Pharmaceutical form:** chewable tablets.

Each tablet contains the following active ingredients calcium carbonate 1250 mg (equivalent to 500 mg of elemental calcium), cholecalciferol (vitamin D3) 5 mcg (200 IU) (as cholecalciferol concentrate - 2 mg), *excipients:* sorbitol - 390 mg; isomalt - 62 mg; povidone - 36.4 mg; magnesium stearate - 6 mg; aspartame - 1 mg; orange oil - 0.97 mg; mono- and diacylglycerols - 0.0008 mg.

**Posology and method of administration:** the product is taken orally during meals, it should be chewed or dissolve in the mouth.

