### **4.2 Inclusion criteria**

A patient should meet all of the following inclusion criteria:

1. Females aged 45 years and older
2. Postmenopausal (absence of menstrual periods for a minimum of 12 months) at the moment of Informed Consent sign.
3. Arterial hypertension grade I / II per ESH/ESC 2013 guidelines (diastolic pressure  $\geq 90$  and  $<110$  mm Hg, systolic pressure  $\geq 140$  and  $<180$  mm Hg).
4. Not achieving BP targets  $<140/90$  mmHg either during antihypertensive therapy or naive.
5. Absence of moxonidine or bisoprolol treatment at least 6 months before the study
6. Osteopenia of lumbar spine and/or proximal part of the femur (osteoporosis T-score from -1 to -2.5 standard deviations [SD]) by X-Ray densitometry.
7. Signed informed consent form to participate in the program.

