**At visit V2:**

- If a patient responds to the selected treatment regimen (BP <180/120 mmHg), the investigator will continue this regimen until the next visit.
- If a patient does not respond to the selected treatment regimen (BP  $\geq$ 180 /120 mmHg), the patient is withdrawn from the study.

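### Section 5.1 continues treatment at V2 and V3 for any BP below 180/120 with no escalation branch, against the <140/90 titration rules in sections 3.6.4, 3.6.5 and 3.8.3.1

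*Combined protocol and SAP*

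**What the plan says.** Section 5.1 sets the action at V2 by one threshold: "If a patient responds to the selected treatment regimen (BP <180/120 mmHg), the investigator will continue this regimen until the next visit". At or above 180/120 the patient is withdrawn. The V3 bullets are the same. Neither visit has a branch that raises a dose or adds a drug.

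Other sections use the <140/90 target:

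- Section 3.6.4, for V2: "If target BP has not been reached, the patient's investigated product dose is titrated according to the study design". Treatment continues unchanged only if target has been reached. Section 3.6.5 repeats this for V3.
- Section 3.8.3.1 prescribes perindopril to patients "who have not reached target BP (<140/90 Hgmm) by V2 (week 8").
- Section 3.1 says that "an ACE inhibitor (perindopril) at a dose of 10 mg/day is added at the 8th week of the study", for patients who missed target after two weeks on the increased dose. The synopsis and sections 3.8.1 and 3.8.2 are softer: perindopril is an option at week 8 where needed.
- The schedule in section 3.4 marks "Dose titration / treatment adjustment" at V1, V2 and V3, without a BP threshold.
- Section 10.3 defines a responder as BP <140/90 at the visit.

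Section 5.1 does escalate earlier, at the telephone contacts in weeks 2 and 4.

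**The concern.** An investigator working from 5.1 and one working from 3.6.4 would treat the same patient differently at V2, and each would be following the protocol. The 5.1 threshold also cannot measure response. Section 4.2 requires "Arterial hypertension grade I / II per ESH/ESC 2013 guidelines", given there as SBP below 180 and DBP below 110, and section 4.4 requires the criteria to be met at the enrollment visit. Every eligible patient is therefore already below 180/120 before her first tablet.

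Two things are at stake. A hypertensive patient can be left above target on an instruction that is correctly followed. And the proportion below 140/90 at V3 and V4, a listed secondary endpoint, can come out lower than the intended regimen would give.

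**Working it through.** The protocol states no figure for this point. The check compares the rules and then works out the timing and the weight of one patient.

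**Rules compared, for BP not at <140/90 but below 180/120 (for example 150/95)**

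| Visit and current treatment | Section 5.1 | Other sections | Express conflict? |
|---|---|---|---|
| V2, 0.4 mg or 5 mg alone | continue | 3.6.4: raise dose; 3.8.3.1: perindopril if not at target by V2 | yes |
| V2, 0.6 mg or 7.5 mg alone | continue | 3.8.3.1: add perindopril; 3.1: same step at week 8 if target was missed after two weeks on this dose | yes |
| V2, maximum dose plus perindopril or losartan | continue | no step left | no |
| V3, 0.4 mg or 5 mg alone | continue | 3.6.5: raise dose | yes |
| V3, 0.6 mg or 7.5 mg alone | continue | 3.6.5: no dose step left; perindopril start at V3 not stated | no, but a gap |

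The V3 rows are limited because 3.6.5 titrates the investigated product, and section 3.8 identifies those products: "Investigated products, moxonidine and bisoprolol, will be provided by the Sponsor". Perindopril is not among them.

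**Who can reach V2 with a step left.** In 5.1 the week-4 perindopril step applies only to patients already on 0.6 mg or 7.5 mg, and the week-2 moxonidine increase is optional. A patient still on the starting dose at week 4, or controlled at week 4 and above target later, has no further escalation route in 5.1.

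**Time without the step.** Nominal visit days are 56 (V2, section 3.6.2), 168 (V3, section 3.6.4) and 336 (V4, section 3.6.5), each ±5 days.

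- V2 to V3: 168 − 56 = 112 days; 112 / 7 = 16 weeks. This applies if 3.6.5 is followed at V3 and a dose step is still available.
- V2 to V4: 336 − 56 = 280 days; 280 / 7 = 40 weeks. This applies if 5.1 is followed at V3 as well.
- V3 to V4: 336 − 168 = 168 days; 168 / 7 = 24 weeks. This applies to a patient first above target at V3 and still on 0.4 mg or 5 mg.

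**Weight of one patient.** Section 3.2 allocates 57 per arm. One patient whom the withheld step would have controlled lowers that arm's V3 or V4 control rate by 1/57 = 1.75, about 1.8 percentage points. If only 100 enrol (section 10.5) in equal arms, it is 1/50 = 2.0 points. Section 10.3 analyses efficacy in per-protocol completers, so the real denominator can be smaller and the weight larger. With 57 planned per arm, 1.8 points is a minimum.

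**What is not touched.** BP at V2 is measured before the V2 decision, so the week-8 rate does not change. The definition of the CTX primary endpoint does not involve this rule.

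**The case against.** The best defence is that 180/120 in 5.1 is only a withdrawal limit, with titration governed by the visit procedures in 3.6.4 and 3.6.5. Section 3.6.2 supports this. Under its treatment-regimens heading the whole ladder is one regimen: "patients receive moxonidine with dose titration up to the maximum, then a patient may be switched to the combination therapy, if necessary". Continuing the regimen could then include the next step. This does not remove the conflict. The 5.1 bullets are directive, they call a BP below 180/120 a response, and they have no <140/90 branch, whereas 3.6.4 makes unchanged treatment conditional on reaching target.

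The second defence is that escalation at weeks 2 and 4 leaves few patients with a step unused at V2, and that section 5.2 allows short-acting agents for hypertensive episodes. That limits the size, possibly to zero, but patients who miss the early steps or lose control later remain uncovered.

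Four stronger readings are tempting, and the documents do not support them:

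- *That every section makes perindopril compulsory on the V2 reading.* Section 3.1 is triggered by failure after two weeks on the increased dose, and the synopsis, 3.8.1 and 3.8.2 are permissive. Only 3.6.4 (study dose) and 3.8.3.1 (perindopril) act on target status at V2 without that qualification.
- *That perindopril is withheld at V3 against the protocol.* No section says it may start at V3.
- *That the 5.1 withdrawal rule contradicts item 6 of section 4.5.* Item 6 is one of several reasons for which a patient may be withdrawn, and item 4, on safety, can cover a never-controlled patient at that level.
- *That the comparison of moxonidine with bisoprolol is biased.* The V2 and V3 bullets are the same for both arms, and no direction of bias is shown.

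**Conclusion.** The V2 bullets of 5.1 are wrong as written. For a patient above target with a step left, they give the opposite instruction to 3.6.4 and 3.8.3.1, and their use of response disagrees with 10.3. At V3 the express conflict is narrower: it is with 3.6.5, for patients still on 0.4 mg or 5 mg. Starting perindopril at V3 is an unanswered question.

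For a V2 patient the step is withheld for 16 weeks, or 40 if 5.1 is also followed at V3. The cost to a V3 or V4 control rate is at least about 1.8 points for each patient whom the step would have controlled. This assumes that a site follows 5.1 over the visit procedures and that the patient has a step left. The documents do not allow the number of such patients to be estimated.

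The study is exploratory and the affected endpoint is secondary, so this is not a threat to the primary result. It deserves correction because it concerns BP control in treated patients and the remedy is cheap.

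**What to change.** Reword the V2 and V3 bullets of 5.1, identically for both arms:

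- **BP <140/90:** continue unchanged.
- **Not at <140/90 but below the withdrawal limit:** escalate as in 3.6.4 and 3.6.5. Raise to moxonidine 0.6 mg or bisoprolol 7.5 mg. At V2, if already at that dose, add perindopril 10 mg, or losartan 50 mg if intolerant. Continue if no step remains.
- **SBP ≥180 and/or DBP ≥120:** withdraw. Stating it this way settles a reading such as 185/100, and 180/120 then serves only as a withdrawal limit.

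Reserve *responds* and *responder* for <140/90, as in 10.3.

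The sponsor should decide whether perindopril may start at V3, because that would be a new rule. If it may, take the final-visit potassium and creatinine sample that section 7.2 describes, since the schedule in 3.4 has none after V3. Redrafting item 6 of 4.5 to match is optional.

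The cost is a wording amendment that needs Ethics Committee approval (sections 12.1 and 13.1). It adds no visits and no drugs. The only possible extra test is the final-visit sample.

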**At visit V3:**

- If a patient responds to the selected treatment regimen (BP <180/120 mmHg), the investigator will continue this regimen until the next visit.
- If a patient does not respond to the selected treatment regimen (BP  $\geq$ 180/120 mmHg), the patient is withdrawn from the study.

**At final visit V4**, the investigator will evaluate the patient response to the treatment and will discontinue all investigated medications. Further treatment is carried out according to the attending physician advice.

**5.2 Fast-acting agents to relieve hypertensive episodes**

During the washout period and the rest of the study, use of short-acting agents to relieve hypertensive episodes, such as captopril and nifedipine, is allowed. However, patients must be instructed to refrain from these medications for 24 hours prior to the study visit in order to obtain accurate blood pressure data. At the visits, the investigator will ask if a patient took any short-acting drugs to relief hypertensive episodes; data and time of the last dose will be documented in the CRF.

**5.3 Investigated treatment withdrawal**

If the investigated treatment should be withdrawn for any reason before the end of the study, gradual investigated products doses reduction is not required. The early treatment withdrawal means the patient is withdrawn from the study.

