#### **4.5 Study withdrawal criteria**

A patient may be withdrawn from the study before the treatment is started, if the investigator discovers deviations from any inclusion criteria, exclusion criteria, or criteria for the treatment initiation. Patients who withdrew before the treatment start (i.e., during screening or washout period), will be substituted with new patients.

In the present study, withdrawal from the study will also mean discontinuation of the investigated treatment.

The patient may be withdrawn from the study due to the following reasons:

1. Withdrawal of the informed consent to participate in the study.
2. Low treatment compliance (<80%).
3. Adverse events that in the investigator's opinion make the treatment continuation impossible, dangerous, or inconsistent with best patient interest and safety. A SAE is not necessarily the cause of early patient withdrawal from the study.
4. According to the investigator, continued participation of the patient in the study threatens the patient's safety.
5. It is necessary to administer treatment prohibited by the study protocol.
6. Failure of the investigated treatment (i.e., recurrent rise of blood pressure  $\geq 180/120$  mmHg after previously achieved target BP level).
7. Death of the patient.
8. Sponsor decision.

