#### **4.6 Early withdrawal procedures**

All patients who were withdrawn from the study early are asked to complete the final visit procedures, if possible. If the decision to terminate the patient participation was made between two scheduled visits, the patient is asked to come for the upcoming scheduled visit, as usual, or make an unscheduled visit.

The reason for the early withdrawal should be indicated in the source documents. If the patient is lost to follow-up, the investigator should make all reasonable efforts to contact the

patient to obtain information on date of withdrawal and reason for the investigated product discontinuation. If the patient cannot be reached, she will be considered as lost to follow-up.

In the case of early investigated product discontinuation due to an adverse event (regardless of whether the event should be immediately reported), the researcher must make every effort to collect information regarding the AE outcome. This information is added to the source documents and CRF, under adverse events section.

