#### **5.4.2 Prohibited treatment**

During the treatment with the investigated product, patients **should not take**:

- Other antihypertensive drugs, except for the investigated products. The only exception is short-acting antihypertensives prescribed by the investigator to relieve hypertensive episodes PRN. These medications should be withheld the day prior to the visit to avoid effects on blood pressure measurement during the visit and evaluation of the investigated treatment efficacy.
- Thiazide diuretics, corticosteroids, bisphosphonates or levothyroxine since these agents are known to affect bone metabolism and BMD.
- Antacids, if the interval between an antacid and the investigated product administration is less than 2 hours.

If there is a need to prescribe the prohibited treatment to a patient or it became known that a patient is receiving the prohibited treatment, the patient is withdrawn from the study.

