#### **5.5 Analysis of compliance**

At every visit, starting with visit V2, the dispensed and returned investigated product is counted, and the patient compliance is assessed. The investigator or his/her authorized representative will count the number of dispensed and returned tablets and document it in the accountability form and CRF. Additionally, date of the first and last product administration, and deviations in the product dosing regimen within the last intervisit interval (if any) will be documented in CRF.

In case of low patient compliance with the investigated treatment (the patient took <80 tablets within the intervisit interval), the patient will be withdrawn from the study.

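### Stopping study drug ends participation, so a consenting stopper need not give a week-48 CTX, and the only planned analysis that could include her is left on weak data

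*Combined protocol and SAP*

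**What the plan says.** Section 5.3 states the rule: "The early treatment withdrawal means the patient is withdrawn from the study". Section 4.5 gives the converse link, that "withdrawal from the study will also mean discontinuation of the investigated treatment".

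Several exits can fall on women who still consent:
- Section 5.1 withdraws a patient at V2 or V3 when blood pressure is 180/120 mmHg or above ("If a patient does not respond to the selected treatment regimen").
- Section 5.4.2 does so once a prohibited drug is needed or "it became known that a patient is receiving the prohibited treatment, the patient is withdrawn from the study".
- Section 5.5 does so for low compliance, judged from tablet counts: "At every visit, starting with visit V2, the dispensed and returned investigated product is counted, and the patient compliance is assessed".
- Section 4.5, reason 6, allows it for "Failure of the investigated treatment (i.e., recurrent rise of blood pressure", which is not tied to a visit.

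Section 4.6 gives partial mitigation: "All patients who were withdrawn from the study early are asked to complete the final visit procedures, if possible". If the decision falls between visits, "the patient is asked to come for the upcoming scheduled visit, as usual, or make an unscheduled visit". No window is set. The final-visit procedures include CTX (section 3.6.6).

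On analysis, sections 6 and 10.3 put efficacy in the PP population. Section 10.2 defines an ITT set requiring V3 or V4 data and brings in non-completers by LOCF. Section 10.1 leaves detail to a statistical analysis plan finalised before data lock.

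**The concern.** The primary endpoint is the change in CTX from V1 to V4. Nothing in the protocol keeps a consenting patient in follow-up to V4 once she is off drug; she is only asked for an exit assessment, at a time that may be far from week 48.

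This matters because the reasons for stopping may be related to outcome and to arm. Blood-pressure failure depends on how well each drug works. Needing a bisphosphonate or corticosteroid bears directly on bone turnover. In an open-label trial, the decision to stop can itself depend on the known treatment. A completers-only analysis cannot reveal such selection. The ITT/LOCF analysis is the only planned one that could include stoppers, and the exit rules determine what data it would carry.

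**Working it through.** **1. Figures in the plan.** There is none to reproduce. Section 10.5 sets 114 patients on feasibility, without a power calculation, and no section gives a dropout rate, SD or effect size.

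**2. When an exit CTX would be taken.** Visits are at weeks 8 (V2), 24 (V3) and 48 (V4). CTX is scheduled at V1, V3 and V4 (section 3.4). The table assumes that the requested exit procedures are done.

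| Stop | CTX taken at | Weeks off drug | In ITT? |
|---|---|---|---|
| BP rule at V2 | week 8, which is 48 − 8 = 40 weeks before the endpoint | 0 | only if the exit is coded V4 |
| Week 9, between visits | week 9, or V3 | 0, or 24 − 9 = 15 | depends on coding, or yes |
| BP rule or tablet count at V3 | week 24 | 0 | yes |
| Week 25, between visits | week 25, or V4 | 0, or 48 − 25 = 23 | yes, from V3 data |
| Tablet count at V4 | week 48 | 0 | yes |

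The plan does not say whether an early exit visit counts as V4. LOCF would treat all of these values as week-48 values.

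**3. How many patients.** Assumption: 10–20% stop, evenly over 48 weeks.
- Stoppers: 114 × 0.10 = 11.4; 114 × 0.20 = 22.8. So at most about 11–23 lack a week-48 CTX.
- Share stopping after V3: (48 − 24)/48 = one half, or 5.7 and 11.4 patients. If all of these attend V4, the number lacking a week-48 CTX falls to about 6–11.

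The even spread is a simplification, since the BP rule and tablet counts act at visits.

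**4. Possible LOCF bias.** Suppose there is no true difference at week 48 and CTX falls by c SD in both arms. Let f be the share of that fall present at a stopper's last observation, and d₁ and d₂ the shares of stoppers in each arm's analysed set. Then

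false difference = c × (1 − f) × (d₁ − d₂).

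| c (SD) | 20% v 10%, f = 0.5 | 20% v 10%, f = 0 | 30% v 10%, f = 0.5 | 30% v 10%, f = 0 |
|---|---|---|---|---|
| 0.3 | 0.015 | 0.03 | 0.03 | 0.06 |
| 0.5 | 0.025 | 0.05 | 0.05 | 0.10 |
| 0.8 | 0.04 | 0.08 | 0.08 | 0.16 |

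The extremes are 0.3 × 0.5 × 0.10 = 0.015 and 0.8 × 1 × 0.20 = 0.16 SD. The arm with more stopping appears to have the smaller fall. The bias is zero if stopping is equal (d₁ = d₂) or if the full week-48 change is already present (f = 1).

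**5. Measures with no V3 value.** In the section 3.4 schedule, bone mineral density (BMD), pulse wave velocity (PWV), intima-media thickness (IMT) and telomerase are taken only at baseline (screening for BMD) and V4. A woman who stops after V3 without an exit assessment is in the ITT set through her V3 CTX. For these four measures she has only baseline to carry forward, which LOCF records as zero change.

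**The case against.** The strongest reply is that no stated efficacy result changes. Efficacy is PP, section 10.2 never assigns the CTX comparison to ITT, and no section gives ITT/LOCF the task of checking for selective stopping. This stands in part. A reader might infer that loose exit timing biases the primary result; the documents do not support that, because PP drops stoppers by any route. The point is narrower: the one analysis set that could include them would rest on poorly defined values.

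A reader might also infer that stoppers leave with no CTX at all. Section 4.6 asks for one. A patient withdrawn at V3 has her scheduled sample that day, and one found non-compliant at V4 is sampled at week 48.

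A third inference is that the harm is dilution of the treatment contrast by off-drug values. That would not justify the change. If all drug effect is lost by week 48, an all-randomised treatment-policy contrast is multiplied by 1 − 0.10 = 0.90 or 1 − 0.20 = 0.80, at least as much dilution as under LOCF. The case rests on selective stopping.

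It is also fair to say that the trial is exploratory, that an on-treatment question is legitimate, and that section 5.4.2 excludes bone-active drugs for good reason. Keeping PP answers this. Finally, a later analysis plan could settle visit coding and replace LOCF, but it cannot recover samples never drawn.

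**Conclusion.** The concern holds in limited form. Stopping drug ends participation, no week-48 CTX is required of a consenting stopper, and ITT/LOCF would carry values differing in week and drug status. The trial therefore has no sound check on selective stopping. This is a worthwhile, inexpensive improvement and not an error in the stated PP analysis, on which exit timing has no effect.

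The size cannot be derived from the documents. The patient counts rest on the assumed 10–20% stopping rate. The 0.015–0.16 SD range further assumes unequal stopping, a common CTX fall and at most half of that fall present at the last observation; with equal stopping that bias vanishes.

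**What to change.** - **Sections 4.5, 4.6 and 5.3, with matching lines in 5.1, 5.4.2 and 5.5:** separate discontinuing treatment from withdrawing from the study. Leave the clinical reasons for stopping drug as they are.
- **Follow-up:** keep consenting stoppers on V3 and V4 as scheduled, with CTX and the other V4 measures. Record treatment after stopping, including the bone-active drugs named in 5.4.2.
- **Early-termination samples:** if a patient declines further visits, label the sample with its actual date and do not code it as V4.
- **Section 10.2:** replace LOCF with an all-randomised analysis of observed CTX, for example a repeated-measures mixed model using V1, V3 and V4, reported beside PP.

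The cost is protocol, consent and analysis wording plus retention effort; the visits and assays are already scheduled for every patient. Some week-48 values will be off drug or on other drugs. The all-randomised result therefore answers a treatment-policy question, and PP remains for the on-drug question.
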